In this study we will monitor vital signs with a novel wireless remote monitoring system, determine the incidence of episodes of AF and assess the usability and acceptability of wCVSM in high-risk patients in various acute conditions. We will conduct two work packages to 1. Obtain data for the generation of virtual digital twins and to quantitatively assess the incidence and pattern distribution of episodes of AF and to 2. Explore user acceptability of the monitoring system and experience of health care professionals in questionnaires and semi-structured interviews.

1. WP1: (Monitoring of vital signs to obtain data for virtual twins to predict clinical and subclinical episodes of AF):

The primary objective of this work package is to determine the incidence of clinical and subclinical episodes of AF in acutely unwell patients and to generate data for the development and validation of virtual twins and clinical decision support tools.

Secondary objectives include:

1. To determine the correlation between number of alerts and occurrence of AF
2. To identify differences in age, gender, length of stay, 30-day mortality, hs-cTn levels, RWMA scores and average National Early Warning (NEWS2) scores in acutely unwell patients
3. To determine the pattern and distribution of AF episodes in acutely unwell patients
4. To identify risk factors for the occurrence of AF episodes
5. To describe the occurrence, incidence and character of alerts registered by wCVSM devices and connected applications (WARD 24).

6. To describe the clinical response to non-cardiovascular alerts and cardiovascular alerts

2. WP2:

We will test the acceptability and usability of wCVSM by conducting questionnaires with patients and health care professionals. We will also conduct semi-structured interviews with health care professionals involved in the care of the study patients to explore their experience with the wCVSM system and the connected software and app. We will develop a thorough implementation guide for the software based on these findings.

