Patients admitted to wards where the WARD247 application is being tested, will be asked to participate. Patients will be asked to complete a questionnaire (Appendix C) to explore their experiences with a remote wireless monitoring system. Health care professionals will participate in semi-structured interviews (Appendix A) and complete the mHealth App Usability Questionnaire (MAUQ) for Standalone mHealth Apps Used by Healthcare Providers a standard questionnaire designed by the University of Pittsburgh (Appendix B). The results and data obtained in this work package will be shared with the WARD24/7 international study team as described in a separate data sharing agreement.

Outcomes for this work package include:

- Number of false alerts
- Number of correct alerts
- MAUQ score
- Semi-quantitative assessment of patient acceptability
- Semi-quantitative assessment of acceptability for nursing and healthcare staff
- Time wCVSM is attached

Study Objectives, Design and Statistics

Research questions and objectives

The **primary research objective** is:

To determine the incidence of clinical and subclinical episodes of AF in acutely unwell patients and to generate data for the development and validation of virtual twins and clinical decision support tools.

The **secondary research objective** is:

To determine patient acceptability and usability for health care professionals of a novel remote monitoring device with automated alert function.

Primary outcome:

The incidence of episodes of AF lasting >30 seconds in acutely unwell and postoperative patients recorded as part of standard clinical care through extended remote wireless patch-based monitoring with or without the use of an alert system (Application).

Secondary outcomes:

Work package 1:

- Length of stay
- Hospital readmissions within 90 days
- Hospital and 90-day Mortality
- Recurrence of AF episodes
- Time spent in AF
- Number of AF episodes
- Complications of AF, e. g. stroke, thromboembolic events
- High sensitivity Troponin concentrations in patients with AF episodes
- Echocardiographic changes in patients with AF episodes

Work package 2:

- MAUQ score
- Percentage change of troponin concentrations in patients with and without episodes of AF
- Time (in hours) wCVSM is attached
- Number of cardiovascular alerts

- Number of non-cardiovascular alerts
- Number of alerts reflecting clinical changes
- Number of alerts reflecting artefacts or non-clinical events

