- RWMA score, atrial size and volume, left ventricular strain rate, standard echocardiographic measurements as per BSE recommendations
- Change in inflammatory markers white cell count, C-reactive protein and procalcitonin over time

Study Design

This is a single centre mixed methods prospective observational study

Statistics

A detailed statistical analysis plan will be developed for the project in line with the objectives for TARGET to achieve the development and validation of dynamic risk prediction tools and virtual health twins.

Sample size considerations:

The primary aim for this study is to generate data for the development of Health Virtual twins as part of the EU Horizon 2023 TARGET project. We will therefore collect a convenience sample of at 1200 patients with a risk of developing episodes of AF of at least 5%. Given evidence from the literature that subclinical episodes that remain undetected may be as high as 30% or more, we expect that in a cohort of 1200 patients at least 60-120 patients will be diagnosed with episodes of AF of at least 30 seconds.

Although the primary aim of the study is to obtain data for the generation of dynamic risk prediction tools and virtual health twins, we will perform a conventional statistical analysis as part of this work:

The primary outcome (incidence of AF episodes >30 sec in acute illness) will be described as ratio of episodes/patient and as percentage of patients having episodes of AF. We will also analyse time spent in AF a percentage of time monitoring was in place, distribution pattern of AF, duration of AF episodes. Occurrence and frequency of premature atrial complexes as precursors of AF episodes.

We will use conventional logistic regression models to establish the correlation and weight between risk factors for AF (e.g. age, cardiovascular comorbidities, organ dysfunction and support, blood pressure, infection status etc.) and occurrence of AF.

Outcomes will be compared in univariate analyses, using parametric or non-parametric test depending on sample distribution.

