Descriptive statistics will be used to describe demographics, frequency of alerts and blood results in patients with and without episodes of AF. Group comparisons will include parametric (T-Test for independent samples) and non-parametric tests (Mann-Whitney-U-Test), depending on sample distributions. For categorical data, Fisher's exact test will be used to examine associations between variables. Monotonic relationships between two numerical variables will be defined using Spearman's rank correlation coefficient.

Where applicable, univariate analysis will be followed by multivariate logistic regression analysis to identify risk factors for the development of AF episodes postoperatively. Cochran–Mantel–Haenszel test (CMH) will be used for the analysis of stratified categorical data, using occurrence of AF >30 seconds as the binary outcome.

Data will be transferred to the data science group at LJMU ([name]) for development and validation of health virtual twins and dynamic risk prediction models in line with the TARGET proposal Work Packages 4 and 5 specific objective (pages 3, SO3 and 34-35, part B of the TARGET proposal): "Development of personalised virtual twin models for dynamic risk prediction of AF and AFRS that consider the patient individual characteristics and medical and health status history. These models are based on novel predisposing factors and will out-perform currently used clinical scores and models." The novel dynamic prediction tools will be compared against conventionally generated logistic regression models.

Sample Size, Selection and Withdrawal of Subjects

Sample size

The primary outcome will be described as ratio of AF episodes/patients. We aim to recruit at least 1200 patients over 40 month with the following characteristics:

- Patients admitted or referred to Critical Care (NOTE-AF ICU)
- Patients admitted to hospital with acute heart failure (NOTE-AF HF)
- Patients admitted to Emergency Services with sepsis or infection (NOTE-AF Sepsis)
- Patients post upper gastrointestinal surgery (NOTE-AF PULSE-GI)
- Patients after surgical vascular interventions (NOTE-AF Vasc)
- Patients with acute respiratory failure (NOTE-AF Resp)
- Patients admitted after acute stroke (NOTE-AF stroke)

We expect to recruit at least 150 patients in each of the above patient groups.

Inclusion criteria for enrolment

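### Comparing length of stay between patients with and without AF by simple two-group tests, the natural reading of the Statistics section, makes stay look longer with AF even if AF has no effect

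*Protocol*

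**What the plan says.** **Outcomes.** Length of stay heads the work package 1 list of secondary outcomes, which also contains "Hospital and 90-day Mortality". Secondary objective 2 of work package 1 is "To identify differences in age, gender, length of stay, 30-day mortality, hs-cTn levels" and two further scores; it does not say between which groups.

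**Tests.** The Statistics section states: "Outcomes will be compared in univariate analyses, using parametric or non-parametric test depending on sample distribution". It then says "Descriptive statistics will be used to describe demographics, frequency of alerts and blood results in patients with and without episodes of AF", and continues directly: "Group comparisons will include parametric (T-Test for independent samples) and non-parametric tests (Mann-Whitney-U-Test), depending on sample distributions", and "For categorical data, Fisher's exact test will be used to examine associations between variables". The multivariable logistic regression and the Cochran-Mantel-Haenszel test that follow have AF as the outcome, so they do not address how AF relates to stay or death.

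**Timing of AF.** Patients in AF or flutter at screening or admission are excluded (Exclusion criteria for enrolment). Monitoring runs for seven days after recruitment (Monitoring), during the hospital stay (synopsis, Study procedure). The only stay requirement is that the expected stay is not under 48 hours. Appendix E also records AF from clinical notes as well as from the wireless monitor, with columns to discharge and day 90.

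**Other methods.** The synopsis mentions multivariable analysis for group comparisons, mixed models and survival analysis, and refers to a SAP. It does not attach survival analysis to stay or mortality. Nowhere is AF described as a time-dependent exposure.

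**The concern.** Every patient starts free of AF and joins the AF group only if an episode occurs while he or she is still alive and in hospital. A patient discharged on day 3 had three days in which to qualify; one who stayed ten days had the full monitoring window. The t, Mann-Whitney and Fisher tests treat the resulting groups as if they were fixed at entry. Time in hospital then helps to decide group membership, and is afterwards compared between the groups.

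For stay, the bias is upward in the AF group. For death it runs the other way, because early deaths fall into the group without AF. The protocol's rationale argues from the literature that brief and undetected AF carries worse outcomes. A longer stay produced only by the grouping could be read as support for that argument.

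**Working it through.** **1. The plan's own figure.** The protocol expects 60-120 AF patients among 1200. 1200 × 0.05 = 60 and 1200 × 0.10 = 120. The 5% is stated; the 10% is implied by the upper figure. The count reproduces and is not disputed. Both rates are used below.

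**2. The mechanism by hand.** Take a seven-day AF risk of 10% with a flat hazard and no link between AF and stay.
- Daily hazard: h = −ln(0.9)/7 = 0.01505.
- Chance of being classed as AF with stay L: 1 − exp(−h × min(L, 7)).
- L = 2 days: 1 − exp(−0.0301) = 3.0%. L of 7 days or more: 10.0%.

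A patient who stays a week is thus about 10.0/2.97 = 3.4 times as likely to be classed as AF as one who stays two days. The protocol says AF after non-cardiac surgery is most frequent in the first 72 hours. If the hazard is three times higher in days 0-3, exposure to day 7 is 3 × 3 + 4 = 13 units, so h = 0.10536/13 = 0.00810 per unit. By day 2 the risk is 1 − exp(−6 × 0.00810) = 4.7%, and the ratio is still about 2.1.

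**3. Size for length of stay.** The protocol gives no stay distribution, so the following are assumptions: log-normal stay, AF unrelated to stay, AF counted to the earlier of day 7 and discharge, 5-10% AF, n = 1200, two-sided 0.05. Each range covers both AF rates and flat or front-loaded AF hazards. Mann-Whitney false-positive rates:

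| Median stay | log-SD 0.75, 2-day floor | log-SD 0.7 | log-SD 0.8, 2-day floor |
|---|---|---|---|
| 5 days | not run | 47-99% | not run |
| 6 days | 28-88% | not run | 30-93% |
| 8 days | 16-71% | 17-71% | 17-72% |
| 10 days | 8-41% | 10-38% | 12-50% |
| 14 days | 5-12% | 5-12% | 9-16% |

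At log-SD 0.7 the spurious median difference is 0.95-1.70 days at a median stay of 5 days, 0.75-1.32 at 8, 0.55-1.00 at 10 and 0.30-0.69 at 14. The t-test is less affected: 28-87%, 11-39%, 8-19% and 5-7% at the same medians. If every patient stays at least 7 days, the rejection rate is 4-6%, which is nominal.

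**4. Mortality.** Assumed 90-day mortality of 10%, 20% or 30%, AF about 10%, no AF effect, Fisher's exact test.
- Constant hazard, AF versus no AF: 9.9% vs 10.0%, 19.4% vs 20.0%, 29.5% vs 30.2%. Rejection 3-4%.
- Deaths weighted early (Weibull shape 0.5): 8.6% vs 10.2%, 16.9% vs 20.3%, 26.1% vs 30.4%. Rejection 7-15%.

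**5. Does a landmark cure it?** Classify AF by day 2 among patients still in hospital and compare residual stay. Rejection was 3.0-7.3% over all scenarios, nominal within simulation error, with a median difference of about 0.0-0.3 day.

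**The case against.** **The contrast is not written down.** A reader might infer that the protocol expressly plans to compare stay and mortality by AF status. It does not. The sentence on comparing outcomes names no groups, the sentence on patients with and without AF covers demographics, alerts and blood results, and objective 2 names no contrast. This stands, and the point is conditional on the reading. But t and Mann-Whitney tests need two groups, there is no randomisation, and the clinical cohorts number seven. Use of the alert application is mentioned only in the primary outcome. AF yes/no is the split named beside the tests.

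**The SAP may settle it.** Handling of a time-dependent exposure is ordinary SAP content, and survival analysis is announced. This stands in part. The protocol already fixes simple tests for outcomes, however, and survival analysis with AF entered as a fixed group would carry the same bias.

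**The size is assumed.** This stands. A false-positive rate near 90% is the top of a range that needs a median stay of about 6 days or less, 10% AF and a flat AF hazard. The cohorts include critical care, stroke and major upper gastrointestinal surgery, where stays may be longer.

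**Mortality.** A reader might infer that a true mortality harm would be reversed. No calculation with a true harm was made, and under no effect the distortion is negligible to modest.

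**Conclusion.** The point holds, conditional on the with/without-AF reading. On that reading, length of stay is biased upward for AF patients with no AF effect. The spurious median difference is roughly 0.4-1.7 days (down to 0.3 under the narrower log-SD of 0.7). The Mann-Whitney error rate runs from far above 5% at a median stay of 6-8 days to near nominal at 14 days. All of this rests on assumed stay distributions and on AF being counted only to day 7. The mortality bias makes AF look protective and matters only if deaths cluster early.

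Two further inferences are not supported. A patient need not be wearing the patch to be counted, since AF in clinical notes is also recorded. Nor can long stays be called either safe or badly biased in general: AF is recorded beyond day 7, but the protocol does not say whether such episodes define the group.

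Severity is moderate. These are secondary comparisons, and no stated decision depends on them.

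**What to change.** In the Statistics section:
1. State the contrast for length of stay and mortality, and the window in which AF counts: the monitored days, to discharge, or to day 90. Say whether AF found only in clinical notes counts.
2. Replace ever/never tests for length of stay with AF as a time-varying exposure, in a cause-specific or multistate model for discharge with death as a competing event. For consistency, use a Cox model with time-varying AF for 90-day death.
3. Alternatively, use an early landmark such as day 2: AF status by then, and residual stay among patients still in hospital.

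The cost is analysis wording and slightly more analysis work. Continuous ECG gives onset times during monitoring, and Appendix E already collects AF documentation, length of stay and mortality. A landmark ignores AF that starts later. A day-7 landmark is a poor choice if stays are short: at a median of 6 days and log-SD 0.75, Φ(ln(7/6)/0.75) = Φ(0.21) ≈ 58% of patients would already have left. Neither approach removes confounding by severity of illness; they remove only the artefact of timing.

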Study procedure	
The study comprises two work packages:
 
Work package 1 (Monitoring for episodes of new onset AF):
 
Over 48-month, period patients with one of the above acute conditions will have vital signs monitored continuously for seven days during their hospital stay using a remote wireless monitoring system (Isansys Lifecare Ltd, Patient Status Engine). Where deemed clinically indicated, routine standard vital signs via stationary monitors will be continued. Surplus blood samples will be collected at the beginning of the monitoring period and then in line with routine blood sampling as clinically indicated. When clinically indicated, extra blood samples will be collected for cardiac biomarkers. Echocardiography will be performed by qualified sonographers where clinically indicated. Data collection will include demographics, routine blood results, diagnoses, past medical history, drug history, interventions, length of hospital stay, anaesthetic risk profiles, quality of life, clinical symptoms.
 
Work package 2 (Assessment of acceptability of and experience with a remote wireless monitoring system connected to an app by patients and health care professionals)
 
Patients in Work Package 2 will be asked to complete a questionnaire to explore their experiences with a remote wireless monitoring system. Health care professionals will participate in semi-structured interviews and complete the mHealth App Usability Questionnaire (MAUQ) for Standalone mHealth Apps Used by Healthcare Providers a standard questionnaire designed by the University of Pittsburgh.

Statistical Methodology and Analysis	
Descriptive statistics (mean, median, frequency of occurrences) will be used to summarise the data, univariable and multivariable analysis will be conducted for comparisons between groups, cluster analysis, generalised linear mixed effects models and survival analysis will be used (see statistical analysis plan). A two-sided p-value of <0.05 will be considered clinically significant.
 
Data will be used further for the application and development of machine learning algorithms, aiming at developing and establishing dynamic clinical decision support tools and virtual twins.

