Patients admitted to hospital either for elective surgery or because they are acutely unwell, represent an opportunity to obtain continuous monitoring data. The data obtained in NOTE-AF will feed into the Horizon European TARGET project ([TARGET: https://target-horizon.eu](https://target-horizon.eu)) which aims to develop multi-scale and multi-organ, dynamic, and interoperable virtual twins of AF patients to accelerate translational research, enabling personalised and cost-effective management. Within TARGET, personalised virtual twin models for dynamic risk prediction of AF and AFRS that take into account the patient individual characteristics and medical and health status history will be developed.

Atrial fibrillation in acute illness

AF is common in patients suffering from acute conditions such as infection, stroke, acute heart failure, acute respiratory failure or following major surgery, in particular vascular and upper gastrointestinal surgery [6-8]. Many of these episodes occur in patients without a history of atrial fibrillation. Episodes of AF during acute conditions represents a clinical deterioration in acutely unwell patients and lead to increased short and long-term morbidity and mortality [9]. Infections and in particular sepsis, are major triggers for AF, especially in patients without a history of this arrhythmia. The term “new-onset atrial fibrillation” has been coined specifically to describe the condition. The incidence of NOAF is estimated

to be between 5-15% in all patients with sepsis [10-15] with some studies reporting even higher incidences of up to 40% in patients admitted with septic shock [14, 16, 17]. Risk factors for the development of NOAF during admission to intensive care include increasing age, male sex, pre-existing cardiovascular disease, acute renal failure, and acute respiratory failure, with sepsis itself conferring a moderate risk for NOAF [18, 19]. NOAF in patients with sepsis carries an increased risk of both in-hospital and ICU mortality [10, 20].

Postoperative atrial fibrillation (POAF)

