POAF is the most frequently reported cardiac arrhythmia following non-cardiac surgery. The incidence of POAF is highly variable but estimated to be between 0.5% to 15% in all non-cardiac procedures [21]. There is significant variability in reported incidences, likely caused by discrepancies in the definition of POAF as well as variation in risk depending on the surgical procedures performed. Upper GI surgery has a particularly high incidence of POAF, it occurs in up to 45.5% in patients undergoing oesophageal resections [1, 22] and is associated with increased 30-day mortality, stroke and hospitalisation. In 18% of cases patients suffer further episodes of AF within one year with 27% of these patients progressing to paroxysmal or persistent AF [1]. The true incidence of POAF after oesophagectomy is unknown, but 31.4% of patients meet hs-cTn criteria diagnostic of perioperative myocardial injury (PMI) [23]. Even patients experiencing only short self-terminating episodes of POAF carry a 5-fold risk of developing continuous POAF and double the risk of stroke and thromboembolic events [24]. POAF is also associated with increased all-cause mortality at 30 days, a 3-fold increased risk of stroke within one-month, a 4-fold increased risk of stroke at one-year, a 4-fold increased risk of myocardial infarction and increased risk of hospitalisation with heart failure.

Following non-cardiac surgery, the incidence of POAF is greatest within the first 72 hours postoperatively [25]. However, occurrence beyond 72 hours is less well defined, likely due to a lack of ECG monitoring and the clinically asymptomatic nature of POAF. AF is conventionally diagnosed by 12-lead ECG recordings demonstrating irregular RR intervals without recognisable p-wave activity with a duration of >30 sec. Recordings from implantable and patch-based cardiac monitoring devices suggest that many patients experience episodes of AF which are not diagnosed clinically [26]. Such episodes are not benign entities: Multiple systematic reviews have demonstrated a 5-fold increased risk of developing clinically relevant forms of AF and a 2-3-fold increased risk of stroke and thromboembolic events [25, 27]. This population of postoperative patients at significant risk of complications will remain unidentified without wCVSM. In this study we will use continuous ECG monitoring integrated into wCVSM systems to identify episodes of AF >30s, independent of their clinical recognition.

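### Comparisons of patients with and without AF are unstratified across seven recruitment groups, so a difference in group mix can be reported as an association with AF

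*Protocol*

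**What the plan says.** The Statistics section first announces univariate comparison of outcomes. It then describes demographics, alerts and blood results in patients with and without AF, and continues: "Group comparisons will include parametric (T-Test for independent samples) and non-parametric tests (Mann-Whitney-U-Test), depending on sample distributions". The next sentence reads: "For categorical data, Fisher's exact test will be used to examine associations between variables". No stratum is attached to either.

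The same section also plans a CMH test for stratified categorical data with AF as the binary outcome, without naming the strata. It plans multivariable logistic regression where applicable, worded for postoperative AF. The risk factors listed are open-ended examples (age, comorbidities, organ dysfunction, infection status and others) and do not include the recruitment group. The Synopsis adds multivariable group comparisons and generalised linear mixed models, refers to the SAP, and states: "A two-sided p-value of <0.05 will be considered clinically significant".

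The Sample size section lists seven groups and says: "We expect to recruit at least 150 patients in each of the above patient groups". On AF risk, the Introduction puts the incidence of new-onset AF at an estimated 5-15% in sepsis ("to be between 5-15% in all patients with sepsis"), with up to 40% reported in septic shock. For postoperative AF it gives 0.5-15% across non-cardiac procedures, and of upper GI surgery it says "it occurs in up to 45.5% in patients undergoing oesophageal resections".

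**The concern.** A two-sample test on the whole cohort asks whether the marker differs between AF and non-AF patients over the mixture of groups that happened to be recruited. If one group has both a higher AF risk and a higher level of the marker, AF patients will on average have higher values even when AF and the marker are unrelated within every group.

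Both ingredients are plausible here. The AF figures quoted in the protocol vary widely. One group is defined by sepsis or infection while inflammatory markers are an outcome, and the Introduction says 31.4% of oesophagectomy patients meet the criteria for perioperative myocardial injury while troponin change with and without AF is an outcome.

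The mix is set by recruitment targets in a convenience sample, so the pooled contrast also depends on how many patients each group supplies. At stake is whether a significant difference in troponin, inflammatory markers, alerts or length of stay says something about AF, or only that more AF patients came from certain groups.

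**Working it through.** **The plan's own figure.** The protocol expects that "at least 60-120 patients will be diagnosed with episodes of AF of at least 30 seconds". Check: 0.05 × 1200 = 60. The upper value needs 10%: 0.10 × 1200 = 120. The groups fit the total: 7 × 150 = 1050, and 1200 / 7 = 171 per group if equal. The protocol gives no power or type I error figure for the AF versus no-AF comparisons, so there is none to reproduce.

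**How group mix enters.** With no within-group association, the expected pooled difference is D = Σ μ_k [P(group k | AF) − P(group k | no AF)], where μ_k is the group mean. D is zero if the means are equal or the AF risks are equal.

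**By hand, one shifted group.** Assumptions: seven groups of 171; AF risk 5% in six and p in upper GI; marker SD 1 within groups; upper GI mean shifted by 0.5 SD. For p = 15%:
- AF patients: 6 × 171 × 0.05 + 171 × 0.15 = 77.0; non-AF: 1197 − 77.0 = 1120.0.
- Upper GI share: 25.65 / 77.0 = 0.333 with AF, 145.35 / 1120.0 = 0.130 without.
- D = 0.5 × (0.333 − 0.130) = 0.102 SD.
- Overall SD = √(1 + 0.25 × 1/7 × 6/7) = 1.015; SE = 1.015 × √(1/77.0 + 1/1120.0) = 0.120.
- D/SE = 0.85, so the chance of |Z| > 1.96 is about 14%.

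The same steps give D/SE = 1.86 and 46% for p = 30% (103 AF patients), and D/SE = 2.72 and 78% for p = 45.5% (129 AF patients). Two simulations of this setting gave 13-15%, 48-49% and 78% for the t-test and 12-14%, 45-46% and 76% for Mann-Whitney. With a 0.25 SD shift the t-test rejected 8-9%, 16% and 29-30%. Group-adjusted tests and CMH by group stayed at 4-6%.

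**A second simulation with graded groups.** Seven groups of 171, AF and marker independent within each group, two-sided 0.05, 1500 runs per setting (error about ±1.1 points near 5%). Three sets of AF risks were used: flat 10%; 5, 6, 7, 8, 10, 12, 15%; and 5, 5, 5, 8, 10, 15, 40%. Expected AF patients are 171 × 0.70 = 120, 171 × 0.63 = 108 and 171 × 0.88 = 150. Group means have the stated between-group SD (within-group SD 1). For Fisher, the log-odds of a binary marker are shifted by the same amounts.

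| AF risk | Group means | t | Mann-Whitney | Fisher |
|---|---|---|---|---|
| flat 10% | SD 0.5, graded | 5.7% | 6.0% | 4.8% |
| 5-15% | equal | 5.6% | 5.8% | 4.3% |
| 5-15% | SD 0.5, weak alignment (r = 0.28) | 8.8% | 9.4% | 5.0% |
| 5-15% | SD 0.2, rising with AF risk | 11.0% | 10.7% | 5.6% |
| 5-15% | SD 0.5, rising with AF risk | 41.1% | 41.2% | 14.3% |
| 5-15% | SD 0.8, rising with AF risk | 67.7% | 68.7% | 25.9% |
| 5-40% | equal | 4.9% | 4.4% | 4.3% |
| 5-40% | SD 0.5, weak alignment (r = 0.21) | 18.5% | 18.5% | 8.2% |
| 5-40% | SD 0.2, rising with AF risk | 47.8% | 46.1% | 14.1% |
| 5-40% | SD 0.5, rising with AF risk | 98.6% | 98.5% | 60.4% |

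**After stratifying or adjusting by group.** Across all settings the linear model with group as a factor rejected 4.2-6.2%, CMH by group 4.6-5.9% and van Elteren 4.3-6.3%.

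**The case against.** The strongest reply is that strata and covariates belong in the SAP, which is not at hand, and that the protocol already plans CMH, multivariable and mixed models. This stands in part: for categorical data CMH is most of the remedy and lacks only a named stratum. It does not dispose of the point. The protocol names specific unstratified tests for these comparisons and no stratified test for continuous data. The logistic model is conditional, is worded for postoperative AF and has AF as its outcome, so it does not adjust a comparison of length of stay or troponin change between AF groups.

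A second reply is that the marginal difference is a legitimate descriptive quantity and the tests are valid for it. That is correct, and it is why the unstratified tests can stay as description. It does not help when the result is read as an association with AF, which the Work package 1 objective of identifying risk factors invites.

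Four stronger readings are tempting but not supported:
- That the tests will reject. They do so above 5% only if the marker varies across groups in line with AF risk, and the protocol gives no marker distribution by group.
- That the protocol documents a several-fold difference in AF risk across all seven groups. The 40% and 45.5% are upper values for subgroups, no separate figure is given for the heart failure, stroke, respiratory or vascular groups, and the protocol attributes part of the postoperative spread to differing definitions.
- That univariate p-values select the variables for the logistic model. The text says only that one analysis follows the other.
- That the group is already recorded. The inclusion criteria admit patients with at least one condition, so groups can overlap, and Appendix E lists admission diagnosis and category but no group field.

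**Conclusion.** The point holds in conditional form and should be corrected. Followed as written, the plan can report a difference in group mix as an association with AF. For continuous markers the rejection rate without any within-group association runs from nominal (flat AF risk or equal marker means), through about 9-19% (weak alignment), to 41% or more when means with a between-group SD of 0.5 rise with AF risk. Fisher's test is less affected in the graded settings: 5-8% with weak alignment and 14-60% with strong alignment at the same spread.

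These sizes depend on the assumed marker shifts, equal and non-overlapping groups, and the chosen AF risks. The 5-40% set implies about 150 AF patients, and the 45.5% case about 129, against the protocol's expectation of at least 60-120, so the 5-15% rows are the more cautious guide. The conclusion that stratification restores about 5% held in every setting tried. The affected analyses are secondary. The primary outcome, described as episodes per patient and percentage of patients, is not touched.

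**What to change.** In the Statistics section:
- Assign each patient to one primary recruitment group at enrolment by a stated allocation rule, since groups can overlap, and add the field to the data collected.
- Name that group as the CMH stratum for categorical AF versus no-AF comparisons.
- For continuous comparisons, use a van Elteren (stratified Wilcoxon) test or a linear model with group as a factor.
- Include the group in the logistic risk-factor model.
- Keep the unstratified t-test, Mann-Whitney and Fisher results, labelled as descriptive.

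The cost is one extra field with its allocation rule, a change of wording, and a few degrees of freedom (six for seven groups). No additional patients are needed.
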